## APPENDIX A: Schedule of Treatment and Evaluations

	Screening -21 Days	Day 1 of each Cycle	Day 4 of each Cycle**	Day 8 of each Cycle	Day 11 of each Cycle**	Day 10-11 of each Cycle 	Day 11-15 of each Cycle 	Day 21 of each Cycle	At end of every even Cycle	Every 8 weeks from Day 1 Cycle 1	Aldox Maintenance 	End of Treatment 	Every 2 or 3 mo. 
Signed informed consent	X												
Review inclusion/exclusion		X											
Medical history 	X												
Physical examination	X	X									X	X	X
Height (cm)	X												
Weight (kg)	X	X									X		
BSA calculation 		X									X		
Vital signs 	X	X									X	X	X
ECOG PS	X	X									X	X	
CT/ MRI scan / tumor measurements 	X 8a									X 	X 	X 	X
ECG	X	X									X	X	X
ECHO (with ejection fraction) or MUGA	X								X 		X 	X	X
CBC w/differential & plt 	X	X		X	X		X	X			X 	X 	X
Coagulation tests (PT, PTT, INR)	X												
Serum chemistries 	X*	X		X 			X 	X 			X 	X 	
Urinalysis 	X											X 	
Serum/urine pregnancy test	X												
Aldoxorubicin and ifosfamide/mesna administration 		X											
Aldoxorubicin administration											X		
Re-fill infusion pump, provide IV anti-emetics and hydration therapy, if necessary			X	X	X								
Stop infusion pump						X	X						
Filgrastim or pegfilgrastim administration 						X	X						
Concomitant medications	X 	X									X	X	
Adverse events		X									X	X	

**NOTE: All assessments must be performed within 72 hr of each specified time parameter, except Cycle 1 (see Section 6 for details).**

\*Arterial blood gas test may be done, if needed, to confirm acid levels. \*\*±2 days

## SYNOPSIS

Name of Sponsor/Company: CytRx Corporation	
Protocol Number: ALDOXORUBICIN-P1/2-STS-03	Phase of Development: 1b/2
Title of the Protocol: An Open-Label Phase 1/2 Study to Investigate the Preliminary Safety and Activity of Aldoxorubicin plus Ifosfamide/Mesna in Subjects with Metastatic, Locally Advanced, or Unresectable Soft Tissue Sarcoma	
Primary Objectives: The primary objective of this study is to determine the preliminary safety of administration of aldoxorubicin in combination with ifosfamide in subjects with metastatic, locally advanced, or unresectable soft tissue sarcoma as measured by the frequency and severity of adverse events (AEs), abnormal findings on physical examination, laboratory tests, vital signs, echocardiograms (ECHO) or multiple-gated acquisition (MUGA) scans, electrocardiogram (ECG) results, and weight.	
Secondary Objectives: The secondary objective of this study is to evaluate the activity of aldoxorubicin in combination with ifosfamide/mesna in this population, assessed by overall response rate, progression-free survival (PFS) and PFS at 4 and 6 months.	
Study Rationale and Significance: Aldoxorubicin is a novel prodrug that binds covalently to albumin in the circulation. The drug is accumulated in tumors and doxorubicin is released in the tumor by cleaving the acid labile linker (EMCH) in the low pH tumor environment. This carrier-linked prodrug has demonstrated enhanced anti-tumor activity with reduced toxicity in several murine models and in patients with soft tissue sarcomas when compared with free doxorubicin.  Patients with metastatic, locally advanced, or unresectable soft tissue sarcomas have a poor prognosis with progression-free survival of around 4-5 months and median overall survival of approximately 15 months after treatment with single agent doxorubicin. Several chemotherapy regimens have been explored as palliative therapy for subjects with advanced soft tissue sarcomas. Combinations of ifosfamide and doxorubicin appear to offer the highest response rates and longest time to progression. However, as currently administered these regimens are quite toxic and have not significantly increased survival in these individuals. Aldoxorubicin in combination with a less toxic schedule for administering ifosfamide may improve the activity of this combination without increasing its toxicity as has been demonstrated for ifosfamide as a single agent.	

Name of Sponsor/Company: CytRx Corporation	
Protocol Number: ALDOXORUBICIN-P1/2-STS-03	Phase of Development: 1b/2
Study Design and Methodology: This is a phase 1b/2 open-label study evaluating the preliminary safety and activity of aldoxorubicin administered at either 170 or 250 mg/m  (125 and 185 mg/m  doxorubicin equivalents) intravenously (IV) on Day 1 every 28 days plus 1 gm/m  /day ifosfamide by continuous intravenous infusion for up to 10-14 days (based on tolerability) via a portable/ambulatory infusion pump using a central line such as port-a-cath or PICC line every 28 days starting on Day 1 of each cycle, with equivalent dose of mesna via IV infusion daily with ifosfamide administration for 6 cycles. A subsequent dose level of aldoxorubicin may be administered if < 2 of 3 or < 3 of 6 subjects experience a DLT during Cycles 1 and 2. The subsequent dose level may not be initiated until all subjects have completed at least 2 cycles at the current dose level and approval is granted by the CytRx Medical Monitor. Treatment with granulocyte colony-stimulating factor (G-CSF) should be administered for all subjects as per investigator's clinical judgment or according to ASCO Guidelines (Appendix E). Note: aldoxorubicin, at higher doses, has been associated with >20% incidence of grade 3 or 4 neutropenia. Subjects with response (CR, PR, or SD) to initial combination therapy may continue with aldoxorubicin alone every 21 days at the same dose as used with the combination until disease progression, unacceptable toxicity or withdrawal of consent.	
The study is being expanded to further evaluate both the safety and efficacy observed to date with this combination. Seven subjects were enrolled in the aldoxorubicin (170 mg/m  ) + ifosfamide/mesna dose group without any dose-limiting toxicities. Similarly, 17 subjects have been enrolled in the aldoxorubicin (250 mg/m  ) + ifosfamide/mesna dose group without any dose-limiting toxicities. The most common Grade 3/4 adverse events across both cohorts have been neutropenia and anemia, both medically manageable. To date, there have been 6 subjects with confirmed partial responses and 10 subjects with stable disease across both dose groups. Ten additional subjects, for a total of 40 subjects, will be added across two cohorts: 1) 250 mg/m  aldoxorubicin + ifosfamide/mesna (10-14 days) dose group in previously untreated subjects (current study design), and 2) 250 mg/m  aldoxorubicin + ifosfamide/mesna at a dose of 1 gm/m  for up to 10 days in previously treated subjects.	
The aldoxorubicin 250 mg/m  + ifosfamide/mesna dose group is being expanded a second time to further assess the preliminary activity and safety of this combination. Thirty-one (31) subjects (22 first-line and 9 previously treated) have been enrolled in the aldoxorubicin (250 mg/m  ) + ifosfamide/mesna dose group without any dose-limiting toxicities. The most common Grade 3/4 adverse events have been neutropenia and anemia, both medically manageable. To date, there have been 4 subjects with confirmed partial responses and 13 subjects with stable disease in the 250 mg/m  + ifosfamide/mesna dose group. Forty additional subjects, for a total of 80 subjects (73 in the 250 mg/m  + ifosfamide/mesna dose group), will be added equally (20 subjects per cohort) across two cohorts: 1) 250 mg/m  aldoxorubicin + ifosfamide/mesna (10-14 days) dose group in previously untreated subjects (current study design), and 2) 250 mg/m  aldoxorubicin + ifosfamide/mesna at a dose of 1 gm/m  for up to 10 days in previously treated subjects.	

Name of Sponsor/Company: CytRx Corporation	
Protocol Number: ALDOXORUBICIN-P1/2-STS-03	Phase of Development: 1b/2
Study Design and Methodology (cont.): Subjects will visit the study site every 28 days for their IV infusions, at which time safety monitoring, including AEs, a directed physical examination, laboratory evaluations (serum chemistry and complete blood count [CBC]), vital signs, weight measurements, ECOG performance status and ECGs will be performed. All subjects will have blood drawn for serum electrolytes to evaluate the anion gap prior to each drug administration. Cardiac function will also be followed periodically using either ECHO or MUGA scans. All subjects will have a CBC on Days 8, 11, 15, and 21 and a basic metabolic panel on Days 8, 15, and 21 at either the study site or at their local laboratory. Subjects will return to the study site on Days 4, 8, and 11 (except for those receiving up to 10 days of ifosfamide treatment) to have their ifosfamide infusion pump re-filled and receive intravenous anti-emetics and hydration therapy, if necessary. Between days 11-15, subjects will return to the study site to have their ifosfamide infusion pump turned off. For those subjects receiving ifosfamide for up to 10 days, they will return to the study site between days 10-11 to have their ifosfamide infusion pump turned off. Treatment with aldoxorubicin and ifosfamide/mesna will continue every 28 days for 6 cycles. Subjects with response (CR, PR, or SD) to initial combination therapy may continue with aldoxorubicin alone every 21 days at the same dose as used with the combination until disease progression is observed, unacceptable toxicity occurs, or consent is withdrawn.  Tumor response will be monitored every 8 weeks ( $\pm$ 5 days) from Cycle 1-Day 1 through week 32, and then every 12 weeks ( $\pm$ 5 days) until disease progression using the Response Evaluation Criteria in Solid Tumors (RECIST) 1.1 criteria. For those subjects who stop treatment for reasons other than disease progression and who do not start another therapy, will be followed 2 months following the End of Treatment scan, and then every 3 months until disease progression. Progression-free survival, progression-free survival at 4 and 6 months will be monitored as other primary objectives.	

Name of Sponsor/Company: CytRx Corporation	
Protocol Number: ALDOXORUBICIN-P1/2-STS-03	Phase of Development: 1b/2
Study Population and Main Criteria for Inclusion/Exclusion:	
Inclusion Criteria:	
Subjects must meet the following criteria to be included in the study:	

 
1. Age between 15-80 years, male or female.
 
2. For subjects without prior therapy, adjuvant or neoadjuvant chemotherapy (including doxorubicin) is allowed if no tumor recurrence for at least 12 months since the last measurement, beginning or end of last chemotherapy.
 
3. For subjects with prior therapy, no more than 2 prior regimens, and no prior exposure to ifosfamide.
 
4. Histologically or cytologically confirmed, locally advanced, unresectable, and/or metastatic soft tissue sarcoma (including rhabdomyosarcoma, Ewing's sarcoma and mixed mesodermal sarcoma), chondrosarcoma or osteosarcoma of intermediate or high grade and gastrointestinal stromal tumors (GIST) (only in subjects that have progressed after receiving treatment with imatinib and sunitinib).
 
5. Capable of providing informed consent and complying with trial procedures.
 
6. ECOG performance status 0-2.
 
7. Life expectancy >12 weeks.
 
8. Measurable tumor lesions according to RECIST 1.1 criteria.
 
9. Women must not be able to become pregnant (eg post-menopausal for at least 1 year, surgically sterile, or practicing adequate birth control methods) for the duration of the study. (Adequate contraception includes: oral contraception, implanted contraception, intrauterine device implanted for at least 3 months, or barrier method in conjunction with spermicide.)
 
10. Males and their female partner(s) of child-bearing potential must use 2 forms of effective contraception (see Inclusion 8 plus condom or vasectomy for males) from the last menstrual period of the female partner during the study treatment and for 6 months after the final dose of study treatment.
 
11. Women of child bearing potential must have a negative serum or urine pregnancy test at the Screening Visit and be non-lactating.
 
12. Geographic accessibility to the site that ensures the subject will be able to keep all study-related appointments.
 
	
Exclusion Criteria:	
Subjects meeting the following criteria will not be enrolled:	

 
1. For subjects without prior therapy, prior chemotherapy unless for adjuvant or neoadjuvant therapy with no tumor recurrence for at least 12 months.
 
2. For subjects with prior therapy, < 2 prior regimens or prior exposure to ifosfamide.
 
3. Palliative surgery and/or radiation treatment less than 30 days prior to enrollment.
 
4. Exposure to any investigational agent within 30 days of enrollment.
 
5. Current Stage 1 or 2 soft tissue sarcomas.
 
6. Current evidence/diagnosis of alveolar soft part sarcoma, dermatofibrosarcoma, Kaposi's sarcoma, clear cell sarcomas and unresectable low grade liposarcomas.
 
7. Anion gap > 16 meq/L or arterial blood pH < 7.30.
 
8. Central nervous system metastasis if symptomatic.
 
9. History of other malignancies except cured basal cell carcinoma, superficial bladder cancer or carcinoma in situ of the cervix unless documented free of cancer for <math>\geq</math> 5 years.
 
10. Laboratory values: Screening serum creatinine <math>>1.5 \times</math> upper limit of normal (ULN), alanine aminotransferase (ALT) <math>> 3 \times</math> ULN or <math>>5 \times</math> ULN if liver metastases are present, total bilirubin <math>>3 \times</math> ULN, absolute neutrophil count <math><1,500/\text{mm}^3</math>, platelet concentration <math><100,000/\text{mm}^3</math>, hematocrit level <math><25\%</math> for females or <math><27\%</math> for males, albumin <math><2 \text{ gm/dL}</math>, coagulation tests (prothrombin time [PT], partial thromboplastin time [PTT], International Normalized Ratio [INR]) <math>>1.5 \times</math> ULN.
 
	

Name of Sponsor/Company: CytRx Corporation	
Protocol Number: ALDOXORUBICIN-P1/2-STS-03	Phase of Development: 1b/2

11. Clinically evident congestive heart failure > class II of the New York Heart Association (NYHA) guidelines.
 
12. Current, serious, clinically significant cardiac arrhythmias, defined as the existence of an absolute arrhythmia or ventricular arrhythmias classified as Lown III, IV or V.
 
13. Baseline QTc >470 msec and/or previous history of QT prolongation while taking other medications. Concomitant use of medications associated with a high incidence of QT prolongation should be used with caution.
 
14. History or signs of active coronary artery disease with or without angina pectoris.
 
15. Serious myocardial dysfunction defined as scintigraphically (eg MUGA, myocardial scintigram) or ultrasound determined absolute left ventricular ejection fraction (LVEF) <45% of predicted.
 
16. History of HIV infection.
 
17. Active, clinically significant serious infection requiring treatment with antibiotics, anti-virals or anti-fungals.
 
18. Major surgery within 21 days prior to enrollment.
 
19. Substance abuse or any condition that might interfere with the subject's participation in the study or in the evaluation of the study results.
 
20. Any condition that is unstable and could jeopardize the subject's participation in the study.
	
Number of Subjects: Up to 80 study subjects will be treated at US study centers.	
Test Product, Dose and Mode of Administration: Lyophilized powder in vials that contain 200 mg of aldoxorubicin reconstituted by adding a solution of 50% ethanol: 50% sterile water, administration completed within 2 hours (of being reconstituted) as a 30 minute IV infusion in Lactated Ringer's solution. Total dose of 170 or 250 mg/m  (125 and 185 mg/m  doxorubicin equivalents).  Ifosfamide single-dose vials for constitution and administration by IVI each contain 1 gram or 3 grams of sterile ifosfamide, USP. Ifosfamide is a chemotherapeutic agent chemically related to the nitrogen mustards and a synthetic analog of cyclophosphamide. Injections are prepared for parenteral use by adding Sterile Water for Injection, USP, or Sterile Bacteriostatic Water for Injection, USP (benzyl alcohol or parabens preserved) to the vial and shaking to dissolve. The reconstituted solution is diluted in 0.9% NaCl or 5% dextrose solution and may be administered as a continuous IV infusion for up to 14 consecutive days.	
Adjunctive Therapy, Dose and Mode of Administration: Mesna Injection is a sterile, nonpyrogenic, aqueous solution of colorless to light pink appearance in clear glass multidose vials for intravenous administration. Mesna injection contains 100 mg/mL mesna, 0.25 mg/mL edetate disodium, sodium hydroxide for pH adjustment and q.s with Water for Injection. Mesna injection multidose vials also contain 10.4 mg/mL of benzyl alcohol as a preservative. The solution has a pH range of 6.5 to 7.4.	
Criteria for Evaluation: 
Activity:  The following activity variables will be evaluated as noted:
 
 
• Progression-free survival
 
• Objective tumor response (RECIST 1.1 criteria)
 
• 4 and 6 month progression-free survival
 
	

Name of Sponsor/Company: CytRx Corporation	
Protocol Number: ALDOXORUBICIN-P1/2-STS-03	Phase of Development: 1b/2
Safety: The following safety variables will be assessed over the duration of the study: 

• Adverse events

• Ability to remain on assigned treatment (tolerability)

• Clinical and laboratory data including physical examinations, vital signs, weight, MUGA/ECHO, ECG results and laboratory test results

• Use of concomitant medications

	
Statistical Methods: In accordance with the modified intention-to-treat principle, all enrolled subjects who enter active treatment and have had at least 1 dose of study medication and 1 post-dose efficacy measurement will be included in the primary efficacy analyses.	
Activity: Tumor response will be monitored every 8 weeks ( $\pm 5$ days) from Cycle 1-Day1 through week 32, and then every 12 weeks ( $\pm 5$ days) until disease progression. Objective response will be evaluated using the Response Evaluation Criteria In Solid Tumors 1.1 (RECIST 1.1).  Changes (i.e., improvements) in tumor measurements from baseline values will be assigned a status of CR or PR. Objective response measurements will comprise the sum of CR plus PR. The overall response rate, as well as the rates for the individual categories of response (i.e., CR, PR, SD, and PD), will be estimated by the percentage of subjects achieving these criteria. For the estimation of progression-free survival a Kaplan-Meier analysis will be performed. The percentage of subjects with complete or partial responses, or stable disease will be evaluated at 4 and 6 months.	
Safety: The safety data will be summarized by treatment group. Total number of AEs leading to withdrawal, and abnormal laboratory tests will be summarized for each cohort. Adverse events, ability to remain on assigned treatment (tolerability), and abnormal findings on physical examinations, vital signs, weight, ECG results, laboratory test results, and use of concomitant medications, will be assessed to characterize the safety profile of the treatment groups. Descriptive statistics denoting the changes from baseline to the final assessment visit with respect to key laboratory parameters and vital signs will also be provided.	

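### The latest synopsis ties contraception to 6 months after the last dose for treated men, but gives treated women no period fixed to the last dose

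*Combined protocol and SAP*

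**What the plan says.** All references are to the latest synopsis, the version that plans up to 80 subjects, and to its Appendix A schedule.

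- **Inclusion item 9 (treated women).** Women must be unable to become pregnant, for example through being post-menopausal, "surgically sterile, or practicing adequate birth control methods) for the duration of the study". No interval after the last dose is given.
- **Inclusion item 10 (treated men and their female partners of child-bearing potential).** Two forms of contraception are required "during the study treatment and for 6 months after the final dose of study treatment".
- **Inclusion item 11.** "Women of child bearing potential must have a negative serum or urine pregnancy test at the Screening Visit and be non-lactating". So women who could conceive are eligible. The item adds an entry check but no period after dosing.
- **Study Design and Methodology, maintenance.** Subjects with CR, PR or SD on the combination may continue aldoxorubicin alone "until disease progression, unacceptable toxicity or withdrawal of consent".
- **Study Design and Methodology (cont.), follow-up.** "For those subjects who stop treatment for reasons other than disease progression and who do not start another therapy, will be followed" at "2 months following the End of Treatment scan, and then every 3 months until disease progression".
- **Appendix A.** The grid has an End of Treatment visit and a later column for visits every 2 or 3 months. The pregnancy test is marked at screening only.

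**The concern.** Men and women in this trial receive the same aldoxorubicin and ifosfamide/mesna. The sponsor wrote a 6-month period after the final dose where the treated subject is the father, but no such period where she is the mother, and the synopsis gives no reason for the difference.

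What is at stake is fetal exposure. Item 9 is the only rule in the available text that limits conception in treated women after entry. If a site takes a woman's participation to end when her scheduled visits end, she could leave the requirement well before 6 months, while a man stopping the same drugs on the same day would remain bound. The matter is one of participant and fetal safety; no endpoint, sample size or analysis depends on it.

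**Working it through.** There is no figure of the plan's to reproduce. The check is a comparison of texts.

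**1. The two end points side by side.**

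| | Treated women (item 9) | Treated men and partners (item 10) |
|---|---|---|
| During treatment | required | required |
| Anchor for the end | the study, undefined | final dose |
| Stated period after the final dose | none | 6 months |

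**2. Can item 10 be read to cover treated women?** No. It is addressed to male subjects and their female partners. A woman who is herself a subject falls under item 9.

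**3. Does the end point in item 9 supply a period after the last dose?** That depends on what counts as the study, which the available text does not define. Taking the follow-up rule in Study Design and Methodology (cont.):

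- A woman who stops without progression and starts no other therapy has follow-up visits until progression. If the study includes those visits, she is covered after her last dose for a time that varies from person to person.
- A woman who stops because of progression, or who starts another therapy, is outside the follow-up rule. The only later contact shown for her is the End of Treatment visit. Its timing relative to the last dose is left to footnote 13 of Appendix A, which is not in the public text.

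**4. Is the second group incidental?** No. Progression is one of the three reasons given for ending maintenance aldoxorubicin, so it is a planned stopping point.

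**5. Is there another safeguard in the available text?** None is visible. Item 11 acts at entry, and the Appendix A grid marks no pregnancy test after screening.

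**6. Was the difference chosen or carried over?** The women's wording is the same in all five synopses: item 8 in the first three, item 9 in the 40-subject and 80-subject versions. Item 10 still sends the reader to inclusion 8 for acceptable methods, although item 8 is now measurable disease. That fits carried-over text but does not prove it.

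**7. To whom does the wording apply?** "Seven subjects were enrolled in the aldoxorubicin" group at 170 mg/m², and "Thirty-one (31) subjects (22 first-line and 9 previously treated) have been enrolled in the aldoxorubicin" group at 250 mg/m². That is 7 + 31 = 38 enrolled, leaving 80 − 38 = 42 places. Because the wording never changed, it governs both groups. Neither is broken down by sex or child-bearing potential.

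**The case against.** The strongest objection is that the public documents are synopses and schedule grids only. The protocol body, the Appendix A footnotes and the consent form may fix a period for women, and their absence here is not a gap in the plan. This stands. It limits the point to what the synopsis says and makes a check of those texts the first step.

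Second, the end point in item 9 is ambiguous rather than short. If the study means the whole trial, the requirement could outlast the final dose by a long time. The follow-up sentence also sits with the tumour-assessment schedule and does not say when a subject's other obligations end. And if footnote 13 places the End of Treatment visit some time after the last dose, even women who progress have some cover. A reader might infer from item 9 that treated women have no contraception requirement at all after the last dose. The documents do not support that; they support only that no period is stated and that early release is the likely reading for women who progress or switch. The objection does not remove the asymmetry, since under any of these readings the women's period is not fixed to the last dose.

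Third, nothing in the available text shows that 6 months is the right length for women, or for men. This also stands. A reader might infer from item 10 that 6 months is the established requirement for both sexes, but it is only a default that the sponsor should confirm.

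**Conclusion.** The point holds as a cheap safety improvement. The latest synopsis states 6 months after the final dose for treated men and their partners, and no period tied to the final dose for treated women on the same drugs. Women who progress or start another therapy may be released from the requirement soon after the last dose; other women may be covered for a variable time.

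This rests on two assumptions: that sites would read the end of the study, for each woman, as the end of her described visits, and that the text not available here does not already set a period. Confidence is therefore medium.

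The number affected cannot be estimated. A reader might take the 42 remaining places as its size. The documents do not support that: it leaves out women among the 38 already enrolled under identical wording, includes men, and says nothing about who will progress or switch therapy.

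**What to change.** 1. Check the protocol body, the Appendix A footnotes (12 and 13 in particular) and the consent form. If they state a period for women after the last dose, carry it into item 9.
2. If they do not, amend item 9 so that contraception runs through study treatment and for at least 6 months after the last dose, matching item 10 unless the sponsor justifies another period. The sponsor should confirm that the length suits women.
3. Apply the rule to women already enrolled, including those on aldoxorubicin maintenance, as well as to those still to enrol. Align the protocol body and consent form, and inform sites and treated women.
4. In the same edit, correct the cross-reference in item 10 from inclusion 8 to inclusion 9.

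The cost is a wording alignment if the period already exists elsewhere; otherwise a short amendment, revised consent text and a site letter. No visit or procedure is added. The downside is a longer contraception commitment for women.

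### Inclusion 3 and Exclusion 2 disagree on the number of prior regimens, so as written only subjects with exactly 2 qualify for the previously treated cohort

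*Combined protocol and SAP*

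**What the plan says.** All references are to the synopsis of the current version (up to 80 subjects) in the combined protocol and SAP, unless stated otherwise.

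- Inclusion Criteria, no. 3: "For subjects with prior therapy, no more than 2 prior regimens, and no prior exposure to ifosfamide".
- Exclusion Criteria, opening line: "Subjects meeting the following criteria will not be enrolled".
- Exclusion Criteria, no. 2: "For subjects with prior therapy, < 2 prior regimens or prior exposure to ifosfamide".
- Exclusion Criteria, no. 1, which governs the other cohort: "For subjects without prior therapy, prior chemotherapy unless for adjuvant or neoadjuvant therapy with no tumor recurrence for at least 12 months".
- Study Design and Methodology, second expansion: "Thirty-one (31) subjects (22 first-line and 9 previously treated) have been enrolled" at 250 mg/m². Forty further subjects "will be added equally (20 subjects per cohort) across two cohorts", the second of which receives ifosfamide/mesna "for up to 10 days in previously treated subjects". No number of prior regimens is given there.

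The synopsis of the preceding version (up to 40 subjects) has the same limits in its Inclusion 3 and Exclusion 2. Neither version, as supplied, says what counts as a prior regimen or explains a two-regimen minimum.

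**The concern.** For subjects with prior therapy, the inclusion criterion sets a ceiling of 2 regimens and the exclusion criterion sets a floor of 2. The two criteria treat a subject with one prior regimen in opposite ways. Exclusion 2 repeats Inclusion 3 on ifosfamide but runs the other way on the regimen count. That looks like a reversed sign, though the documents do not confirm it.

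At stake is who enters one of the two expansion cohorts. A site that applies Exclusion 2 literally turns one-regimen subjects away. A site that works from Inclusion 3 enrols them and breaches an exclusion criterion. The cohort's safety results (the primary objective) and its response rate and progression-free survival (secondary, descriptive) would then describe either a two-regimen population or a mix of one and two regimens. Prior treatment bears on how such results are read, so a reader needs to know which population it is.

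**Working it through.** **Eligibility logic.** Let k be the number of prior regimens, for a subject with prior therapy and no ifosfamide. Inclusion 3 requires k ≤ 2. Exclusion 2 bars k < 2.

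| k | Meets Inclusion 3 | Barred by Exclusion 2 | Eligible as written | Eligible on Inclusion 3 alone |
|---|---|---|---|---|
| 1 | yes | yes | no | yes |
| 2 | yes | no | yes | yes |
| 3 or more | no | no | no | no |

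The eligible set is {2} as written and {1, 2} on Inclusion 3 alone.

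**Is there another way in for k = 1?** Not after one chemotherapy regimen for advanced disease. For the untreated cohort, Exclusion 1 permits only adjuvant or neoadjuvant chemotherapy with at least 12 months without recurrence. A subject whose only chemotherapy meets that condition can still enter as untreated.

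**Could the sign be a text-reading fault?** This is unlikely. The same sign stands in two successive versions, and the current exclusion list contains both < and > elsewhere. Between the two versions the sponsor edited Inclusion 3, removing a sentence on doxorubicin exposure, and the mismatch remained.

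**Does the GIST criterion explain a floor of 2?** Inclusion 4 requires progression after imatinib and sunitinib, so GIST subjects may already count 2 regimens. That requirement covers GIST only, whereas Exclusion 2 covers every subject with prior therapy.

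**The plan's totals, reproduced.**

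- Enrolled at 250 mg/m²: 22 + 9 = 31.
- Places at 250 mg/m² under the preceding ceiling of 40, with 7 subjects at 170 mg/m²: 40 − 7 = 33.
- After the second expansion: 33 + 40 = 73 at 250 mg/m², and 7 + 73 = 80 in all. Both match the stated figures.
- Unfilled places under the preceding ceiling: 33 − 31 = 2. Their cohort is not stated.

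**Size of the cohort concerned.**

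- Still to be added: 20 of 40 = 50% of the second expansion.
- Enrolled plus to be added: 9 + 20 = 29, and 29/73 = 39.7% of the 250 mg/m² group.
- If both unfilled places also went to previously treated subjects: 31/73 = 42.5%.

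These are shares of the cohort that the rule governs. They do not estimate how many subjects are wrongly refused or enrolled. That number depends on the distribution of prior regimens, which the documents do not give.

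**The case against.** The strongest reply is that the rule is determinate. Inclusion and exclusion lists apply together, and it is normal for a subject to meet an inclusion and still be barred by an exclusion. Read literally, the plan asks for exactly 2 prior regimens, and the phrase previously treated is only a summary that a narrower criterion does not contradict. This stands as logic: the criteria can both be met at k = 2 and the cohort is not empty. It does not explain why an exact requirement would be written as a maximum in one list and a minimum in the other, with no mention in the design text.

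Other points stand as limits:

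- Only the synopses and Appendix A are supplied. A full eligibility section might settle the point or define a regimen. The synopsis would still need correction if it differed.
- With regimen undefined, the practical effect may be smaller than {2} against {1, 2} suggests. If adjuvant chemotherapy counts, a subject with adjuvant therapy plus one line for advanced disease already has 2. The status of a single prior non-chemotherapy regimen is also unclear, because Exclusion 1 speaks of chemotherapy.
- Nine previously treated subjects were enrolled under the same pair of criteria, so the text did not block accrual. Their regimen counts are not reported.
- The efficacy set under Statistical Methods depends on enrolment, dosing and one post-dose efficacy measurement. An eligibility deviation does not by itself remove a subject, and no test is affected.

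None of these removes the mismatch between the two criteria.

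**Conclusion.** The concern holds. As written, only subjects with exactly 2 prior regimens qualify, against 1 or 2 under Inclusion 3 alone. The mismatch governs 20 places still to be filled and the classification of 9 subjects already enrolled, 29 in all. It must be fixed because an enrolment rule in force invites inconsistent application and leaves the cohort's population unclear. Sample size and hypothesis tests are not affected.

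Confidence is high for the mismatch in the synopsis. That it is a reversed inequality is an inference from the wording. The conclusion assumes that the synopsis criteria are the ones sites apply, and that a subject with prior therapy has had at least one regimen.

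**What to change.** Reconcile Inclusion 3 and Exclusion 2 by amendment so that both state the range the sponsor intends:

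- If 1 or 2 prior regimens is intended, reverse the inequality in Exclusion 2.
- If exactly 2 is intended, say so in Inclusion 3 and in the cohort description under Study Design and Methodology.

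In either case, define what counts as a prior regimen, including how adjuvant or neoadjuvant chemotherapy and non-chemotherapy treatment are counted. Align any full eligibility section with the synopsis. Then check the 9 previously treated subjects, and any enrolled since, against the confirmed rule, record deviations, and describe the cohort's population accordingly in the report.

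The cost is a short text amendment and a check of 9 existing records, plus any added since. No patients or procedures are added, and the totals of 73 and 80 stay as they are.
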